APPENDIX E: DRAIZE SCALE

To be completed by the person who removes the devices (PI, Co-I, or clinical coordinator)

Sensing Cannula (LEFT)

DRAIZE SCALE At END OF VISIT	 0=No erythema  1=Very slight, barely perceptible erythema  2=Well defined erythema  3=Moderate erythema  4=Severe erythema, Beet redness to slight eschar formation	 0=No edema  1=Very slight, barely perceptible edema  2=Well defined edema  3=Moderate edema, raised approx. 1mm  4=Severe edema, raised >1mm and beyond exposure area
---	---	---

Sensing Cannula (RIGHT)

DRAIZE SCALE At END OF VISIT	 0=No erythema  1=Very slight, barely perceptible erythema  2=Well defined erythema  3=Moderate erythema  4=Severe erythema, Beet redness to slight eschar formation	 0=No edema  1=Very slight, barely perceptible edema  2=Well defined edema  3=Moderate edema, raised approx. 1mm  4=Severe edema, raised >1mm and beyond exposure area
---	---	---

Appendix F: Visual Analog Scale (VAS) for PDT Sensor Site Discomfort

Investigative Site Instructions: The subject should complete the VAS for PDT sensor site 15 minutes and 2 hours after sensor insertion and at the end of the study. The subject completes the VAS by drawing a single vertical line through the scale corresponding to the perceived intensity (severity) of discomfort according to the instructions below. At the 15 minute time point, the goal is for the subject to report the amount of discomfort, if any, associated with needle insertion. For the later time points, the goal is for the subject to report the amount of discomfort, if any, remaining at each time point, as opposed to reporting the transient pain associated with needle insertion.

Note: If a subject is unable to physically complete the questionnaire, the subject will indicate the point on the VAS corresponding to their level of discomfort, and study staff will enter a vertical line at that point. Documentation will be provided on each completed questionnaire as to who completed the form.

Please verify the length of the VAS line to be 100-mm before providing it to the subject.

Subject Instructions: Please draw a single vertical line through the scale below that corresponds to the intensity (severity) of any discomfort you have felt. At the 15 minute time point after insertion, please describe your pain from the insertion of the sensors. At the 2 hours and end of study time points, please describe any pain you have experienced since the devices were inserted.

Discomfort could include stinging, burning, tingling, throbbing or pain. The further to the right you make your vertical mark, indicates the more intense discomfort you are feeling.

You should normally draw a straight line across the scale to indicate your current level of discomfort. However, if you are currently feeling no discomfort, you should circle the vertical line on the left end of scale (above the word “no”). If you are currently feeling the worst discomfort possible, you should circle the vertical line on the right end of the scale.

No Discomfort

Worst Possible Discomfort

References

- 1. Thabit H, et al., Home use of closed-loop insulin delivery for overnight glucose control in adults with type 1 diabetes: A 4-week, multicentre, randomised crossover study. Lancet Diabetes Endocrinol 2014 Sep;2(9):701-709**

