- To assess the glucose control achieved in adults with type 1 diabetes with the use of the OHSU closed-loop system.
- To assess the tolerability of the PDT glucose sensor.

Study Hypothesis:

We propose that the accuracy of the PDT glucose sensor is not impacted by the delivery of lispro insulin as compared to a saline placebo.

Endpoints**Primary Endpoints**

- Sensor accuracy as determined by mean absolute difference (MAD) for reference YSI venous blood glucose values ≤ 75 mg/dL and mean absolute relative difference for reference YSI venous blood glucose values >75 mg/dL

Secondary Endpoints (duration: entire study):

- Percent of time with sensed glucose between 70 – 180 mg/dl (based on Dexcom G5 CGM)
- Percent of time with sensed glucose <70 mg/dL (based on Dexcom G5 CGM)
- Percent of time with sensed glucose <54 mg/dl (based on Dexcom G5 CGM)
- Percent of time with sensed glucose >250 mg/dL (based on Dexcom G5 CGM)
- Mean sensed glucose (based on Dexcom G5 CGM)
- Number of carbohydrate treatments (defined as 15 or 20 grams of carbohydrate)
- Total amount of insulin delivered (in units/kg)

- Mean score on visual analog scale at 15 and 120 minutes after insertion, and at end of study
- Mean score on Draize scale at end of study

Study Type

This is a single center, one treatment trial designed to compare the sensor accuracy of the PDT sensing catheter when utilized to deliver lispro insulin as compared to a saline control.

Study Population

Study population will be adults with type 1 diabetes, ages 21 – 65 years of age. Younger subjects are excluded as it is appropriate to assess safety first in the adult population. 10 subjects will be recruited to participate in studies.

Power Analysis

Since data have not previously been obtained in humans (variance is unknown), this study is exploratory and not powered.

Protocol Summary:

[figure not shown]
Subjects will undergo one 12 hour inpatient study. During this intervention visit, subjects will wear two t:slim insulin pumps to deliver insulin or saline through two investigational PDT glucose sensing cannulas, and a Dexcom G5 CGM to measure glucose. The subject will come to

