After preparation of the skin with isopropyl alcohol followed by Chloraprep One-Step (2% chlorhexidine gluconate and 70% isopropyl alcohol), the two investigational PDT glucose sensing cannulas will be inserted subcutaneously in the abdomen, each at least 5 cm from the subject's insulin cannula and at least 5 cm from one another. For subjects allergic to Chloraprep, isopropyl alcohol will be used. The study investigator (PI or co-investigator, i.e. physician or nurse practitioner who has been trained in internal medicine) will manually insert each cannula into the subcutaneous tissue or will insert the cannula with the aid of a spring-operated insertion device. To ensure proper cannula insertion, a written manual and direct in-person training

(including troubleshooting) will be provided by Pacific Diabetes Technologies. The rigid stainless steel cannula will extend 12 mm into the tissue at a 35-45 degree angle (depth beneath skin surface, approximately 7-8 mm). After insertion, a small amount of saline (0.5 ml) will be delivered through each cannula to verify patency. In between usages, the insertion device will be thoroughly cleaned with SaniCloth AF-3 wipes.

The cannula is attached to a sensor housing unit which is affixed to the skin with acrylate-based adhesive tape. An Electronic Module which includes a telemetry unit is connected to the sensor housing. In between use on study subjects, the reusable telemetry unit will be thoroughly cleaned with SaniCloth AF-3 disinfecting wipes. After insertion, the subject will be instructed to avoid vigorous activity until the sensing cannula is removed at the end of the study. The subject will also be asked to keep the device dry. Sensor data (electrical current proportional to glucose level) will be stored within the body-worn electronic module at least once every minute. Sensor data from these investigational sensors will not be used to control the FMPD single hormone algorithm or insulin dosing at any time. The subject will not be able to view the sensor output. A visual analog scale and questionnaire will be given to assess tolerability and pain of the glucose sensing cannulas at 15 and 120 minutes after insertion and just before the glucose sensing cannulas are removed at the end of the study (see Appendix D).

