One t:slim infusion pump (Tandem® Diabetes Care) will be filled with lispro insulin and another will be filled with normal saline. Each pump will be attached to one of the PDT sensing cannulas. See **Figure 2** below for a diagram of the system design. Subjects will disconnect his/her own pump and remove his/her own insulin infusion set once insulin delivery has started via the t:slim pump. Note: The Zephyr Biopatch will not be used in this study to push heart rate data into the APC system to enable exercise detection.

Figure 2: Closed-loop System Design

An 18-22 gauge IV catheter will be placed for measuring blood glucose concentration. When closed loop study is started, a small amount of blood will be collected every 15 minutes until discharge from the unit at 6pm. A heating pad will be placed on the subject's arm to facilitate blood draws and to arterialize venous blood, which allows for frequent measurement of blood glucose and to prevent spurious decline of venous blood glucose from glucose uptake by muscle and fat during slow capillary flow. These arterialized venous samples will be analyzed using a Yellow Springs Instrument (YSI) 2300D Stat Plus Analyzer to obtain a glucose level. In the event the YSI is not available, the sample will be analyzed using a Contour Next blood glucose meter. Normal saline will be infused at a rate of ~25 ml/hr to keep the IV catheter patent. It is possible that the IV catheter will not remain patent, in which case another will be placed. In a blood-sparing technique, venous blood will be withdrawn from the IV catheter using a double stop-cock method. One side of the stop-cock is used to pull ~ 5 mL of saline-blood admixture. The other side of the stop-cock is used to pull approximately 0.5 ml for collection with the saline-blood admixture re-infused after collection. The double stop-cock method is a fully closed system apart from the very brief interval at the time of a blood sample where a new sterile syringe is connected to collect the next sample. This procedure is performed by a research nurse. There will be ~18-20 ml of blood collected per study with a maximum blood draw volume of 30 mL.

After the Dexcom G5 warm-up period is completed, the research staff will initialize the system and begin the closed-loop study. The second t:slim pump will deliver normal saline at the same rate as the insulin pump. The study investigator will then depart but remain on call.

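### Appendix F collects one discomfort mark per time point for two PDT cannulas worn together, so the VAS endpoint is an undefined blend of two sites and not a per-sensor score (minor)

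*Combined protocol and SAP*

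**What the plan says.** The relevant secondary objective is "To assess the tolerability of the PDT glucose sensor". The endpoint that serves it is listed under Secondary Endpoints as "Mean score on visual analog scale at 15 and 120 minutes after insertion, and at end of study". No side, site or fluid is named.

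Under 12 hour Treatment Visit, "the two investigational PDT glucose sensing cannulas will be inserted subcutaneously in the abdomen", and then "Each pump will be attached to one of the PDT sensing cannulas", with one pump holding lispro and the other normal saline. The same section provides for a single scale covering both: "A visual analog scale and questionnaire will be given to assess tolerability and pain of the glucose sensing cannulas at 15 and 120 minutes".

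Appendix F gives the subject one scale and asks: "Please draw a single vertical line through the scale below that corresponds to the intensity (severity) of any discomfort you have felt". It continues: "At the 15 minute time point after insertion, please describe your pain from the insertion of the sensors". For the two later ratings it again refers to the devices in the plural. It has no left/right field and does not ask for one form per site.

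The other two tolerability forms do separate the sites. Appendix D has left and right answers throughout, at 15 minutes, 2 hours and end of study. Appendix E has one block that begins "Sensing Cannula (LEFT" and a matching block for the right.

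**The concern.** The objective concerns the sensor, and Appendix C describes the device as one sensing cannula connected to one pump. The VAS form rates two insertions and two infusates with one mark. A subject with one painful and one painless site has to reduce them to a single number, and nothing says whether that number should be the worse site, the average, or something else. Different subjects may do this differently.

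The Data Analysis section intends the tolerability scores to guide later changes to the device. A millimetre score that cannot be attributed to a device serves that purpose poorly, and marks already made cannot be separated afterwards.

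**Working it through.** The plan states no figure for the VAS (no SD, power or precision), so there is none to reproduce. The check compares the forms, counts scores, and works an illustrative calculation.

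**1. The three tolerability forms**

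| Form | Times | Recorded by side? |
|---|---|---|
| Questionnaire, Appendix D | 15 min, 2 h, end of study | Yes |
| Draize, Appendix E | End of visit | Yes |
| VAS, Appendix F | 15 min, 2 h, end of study | No |

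**2. Scores collected** (10 subjects, from Study Population; 3 time points, from Secondary Endpoints)

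- As written: 10 × 3 × 1 = 30 scores, none attributable to a site.
- With one scale per cannula: 10 × 3 × 2 = 60 scores, or 10 within-subject pairs at each time point.

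**3. One mark does not identify two site scores** (invented values, in mm)

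| Lispro site | Saline site | Mark if worse site | Mark if average | Difference |
|---|---|---|---|---|
| 40 | 0 | 40 | 20 | +40 |
| 0 | 40 | 40 | 20 | −40 |
| 20 | 20 | 20 | 20 | 0 |
| 40 | 40 | 40 | 40 | 0 |

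A mark of 40 under the worse-site rule fits rows 1, 2 and 4. A mark of 20 under averaging fits rows 1, 2 and 3. Neither rule recovers the individual site scores. This result needs no distributional assumption.

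**4. Possible size of the distortion**

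Assume the two site scores X1 and X2 are bivariate normal with a common mean, common SD and correlation r, and that the subject marks the worse site.

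- max(X1, X2) = (X1 + X2)/2 + |X1 − X2|/2.
- X1 − X2 has mean 0 and variance 2·SD²·(1 − r), so E|X1 − X2| = 2·SD·√((1 − r)/π).
- The expected excess over the single-site mean is therefore SD·√((1 − r)/π).

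| r | Factor √((1 − r)/π) | SD 10 mm | SD 20 mm |
|---|---|---|---|
| 0 | 0.564 | 5.6 mm | 11.3 mm |
| 0.5 | 0.399 | 4.0 mm | 8.0 mm |
| 0.8 | 0.252 | 2.5 mm | 5.0 mm |

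If subjects average the sites, E[(X1 + X2)/2] equals the single-site mean and the excess is zero. SD, r, normality and the marking rule are all assumptions.

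**5. What two scales would support**

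With 10 pairs, the 95% confidence interval for a paired mean difference has half-width t(0.975, 9)/√10 = 0.72 SD of the difference. At 80% power and two-sided 0.05 (assumed here; the plan sets no level for the VAS), the detectable difference by paired t is about 1.00 SD of the difference. A lispro-minus-saline contrast would therefore be descriptive only.

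**The case against.** **Site-level discomfort is already collected.** Appendix D records severity and duration by side at the same three times, and Appendix E records skin reaction by side. A subject with one painful and one painless site would show up there. This stands as real mitigation, and a reader should not infer that tolerability by site is lost. What is lost is the by-site millimetre score. The ordinal categories cannot reproduce the listed endpoint, which is a VAS mean.

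**One form per site is not excluded.** The title of Appendix F and its staff instruction refer to the sensor site in the singular, and graphics may have been lost in text extraction. The objection has some force. Against it, the anchors appear once, the subject instructions are plural, the treatment-visit text provides for one scale, and no side label or per-site instruction is given. If staff did use separate forms, practice could differ between subjects, and that would also need correcting.

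**The tempting stronger reading.** A reader might infer that the form defeats a planned comparison of lispro and saline discomfort. The documents do not support this. No objective, endpoint or analysis compares tolerability by fluid; only sensing accuracy and calibration are compared that way. Even with two scales the contrast would be weak: there are 10 subjects in a study described as exploratory and not powered, with no stated randomisation of side and no stated blinding of subjects to which pump holds insulin.

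**The millimetre figures rest on assumptions.** This is correct. The scale is bounded at no discomfort, so normality is doubtful, and the marking rule is unknown. Any overstatement would also be in the conservative direction for a tolerability claim.

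**Conclusion.** The point holds as a minor defect in how a descriptive secondary endpoint is measured. Followed as written, Appendix F yields 30 ratings of a pair of devices and no per-sensor discomfort score, although the objective concerns the sensor and the two companion forms separate the sites. That conclusion rests on the wording and layout of the forms alone.

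The size of any distortion cannot be fixed from the documents. It is zero if subjects average the sites. If they mark the worse site, it is 2.5 to 11.3 mm under the assumed SD of 10 to 20 mm and r of 0 to 0.8. That range is an illustration and should not be read as an estimate of bias in this trial. The accuracy endpoints are unaffected.

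**What to change.** - Put two labelled 100-mm lines, left and right, on Appendix F at all three time points, matching Appendices D and E.
- Align the treatment-visit text and the Appendix F instructions so that both ask for one rating per cannula.
- Record on the CRF which side carried lispro. The documents state no rule or record linking side to fluid, so side labels alone would not identify it.
- Define the endpoint as the per-cannula score, and allow for two scores per subject, for example by averaging within subject before computing the standard error. The 20 scores at a time point should not be treated as independent.
- If the within-subject lispro-minus-saline difference at end of study is reported, label it descriptive and exploratory.
- In the same revision, settle the recall period. For the later ratings Appendix F asks variously for discomfort still remaining, pain since insertion, and the current level. Two lines would otherwise inherit that ambiguity.

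Cost: a one-page form change, one CRF field, and a few seconds per time point. No extra visit or staff is needed.

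### At 2 hours and end of study, the VAS form asks for both current discomfort and any pain since insertion, so the later VAS means can mix the two

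*Combined protocol and SAP*

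**What the plan says.** The Endpoints section lists the mean VAS score at 15 minutes, 120 minutes and end of study as a secondary endpoint. Sensor tolerability is a secondary objective. The Data Analysis section says that tolerability and skin scores will inform later changes to the device.

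Appendix F holds the VAS form. For the later time points, its instructions to the site state that "the goal is for the subject to report the amount of discomfort, if any, remaining at each time point". The same sentence sets brief pain from the needle aside: "as opposed to reporting the transient pain associated with needle insertion".

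The instructions to the subject open by asking for a mark that "corresponds to the intensity (severity) of any discomfort you have felt". At 15 minutes the subject is asked: "please describe your pain from the insertion of the sensors". At 2 hours and end of study the request is: "please describe any pain you have experienced since the devices were inserted".

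The marking directions then turn to the present. A mark further to the right "indicates the more intense discomfort you are feeling". The general rule is "You should normally draw a straight line across the scale to indicate your current level of discomfort", and for the zero end "if you are currently feeling no discomfort, you should circle the vertical line on the left end of scale".

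**The concern.** At 2 hours and at end of study the subject makes one mark under two definitions. One is the state at that moment; the other is anything felt since the devices went in. Two subjects with the same history can each follow the form faithfully and give different scores. The mark does not show which instruction was followed, so the mixture cannot be separated from the VAS data afterwards.

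What is at stake is the meaning of two of the three VAS means. If they are to guide design changes that reduce discomfort, the reader needs to know whether a non-zero mean reflects discomfort that persists or discomfort that occurred and resolved.

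**Working it through.** The plan gives no VAS figure to reproduce, so the check is a comparison of texts.

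**1. What each instruction asks for at 2 hours and end of study**

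| Source in Appendix F | Quantity asked for | Score if discomfort has resolved |
|---|---|---|
| Site instructions, goal for later times | Discomfort remaining | 0 |
| Subject instructions, opening sentence | Discomfort felt, no period given | Above 0 |
| Subject instructions, sentence for these times | Pain since insertion | Above 0 |
| Subject instructions, marking rule and zero end | Current discomfort | 0 |

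The instructions agree for a subject who has had no discomfort. They can also agree for one whose discomfort is unchanged. They part for a subject whose discomfort has eased or gone.

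**2. Whether another section settles it**

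- Endpoints: names the times, not the recall period.
- 12 hour Treatment Visit: says when the VAS and questionnaire are given and refers to Appendix D. That appendix is the categorical questionnaire and does not govern the VAS line.
- Data Analysis: says that VAS scores will be collected, with no definition.
- Appendix D, 2-hour part: asks about discomfort after the first 15 minutes, separately for left and right, and has a response for discomfort that is still present.
- Appendix D, end-of-study part: asks about the whole period after insertion, by severity and duration, and has no response for discomfort that is still present.

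None of these changes the VAS wording. Appendix D gives a partial cross-check at 2 hours and a weaker one at the end.

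**3. Direction and form of the effect**

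Take one mark per subject at each time, with n = 10 subjects. Suppose k of them had discomfort of P mm that has since resolved and score it by recall. Relative to the site goal, the mean rises by

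shift = k × P / n.

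Neither k nor P is in the documents. For illustration only, assume k = 3 and P between 10 and 40 mm: 3 × 10 / 10 = 3 mm, and 3 × 40 / 10 = 12 mm. With k = 0 the shift is 0; with k = 10 it equals P. This shows how the mixing works and that its direction is upward. It is not an estimate.

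**4. The 15-minute mark**

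Here the site goal and the time-specific subject sentence agree on insertion pain. The marking rule and zero end are not restricted by time, however, so a literal reader whose insertion pain has already passed could mark 0. This is a lesser ambiguity.

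**The case against.** The strongest reply is that the intended measure is stated. The site goal, the marking rule and both ends of the scale all point to the present. Only the opening sentence and the sentence for the later times depart from it. On that view this is a wording slip against a declared aim. That is fair, and the claim that the endpoint is undefined would go too far. The slip still matters, because the subject draws the line from the subject text, and that text contains both definitions.

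Other points in the plan's favour also stand. The study is exploratory and unpowered, all subjects get the same form, and no VAS test or insulin-versus-saline VAS comparison is described.

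A reader might infer three stronger things that the documents do not support:

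- **That the later scores will include insertion pain.** The subject text does not exclude it, but the preceding sentence assigns insertion pain to 15 minutes, and the later sentence reads naturally as the period after insertion. The conflict between current and cumulative discomfort does not depend on this.
- **That the 15-minute mean is biased downward.** The marking rule is phrased as a default, which the specific request can override. The zero-end direction lacks that qualifier, so a small edit is worthwhile, but no bias is shown.
- **That the length of the recall period measures the error.** Hours since insertion give no score in mm.

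**Conclusion.** The VAS subject instructions for 2 hours and end of study are wrong as written: they contradict both the site goal and the form's own marking directions. Resolved discomfort scores 0 under one and above 0 under the other, so the later means can mix current and cumulative discomfort. For resolved discomfort, the direction relative to the site goal is upward. The size in mm cannot be estimated from the documents.

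The point is minor. It touches one secondary tolerability endpoint and leaves the primary accuracy endpoint alone. It is partly offset by Appendix D, more at 2 hours than at end of study. The conclusion rests on the Appendix F text and on the absence of any resolving rule elsewhere; it needs no numerical assumption.

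**What to change.** Before the form is used, revise the subject instructions in Appendix F:

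- At 2 hours and end of study, ask only for discomfort felt now. For those times, remove the request for any discomfort felt and the request for pain since insertion.
- Do not add an instruction to leave out insertion pain. The site goal sets aside only transient pain, and soreness from insertion that still remains counts under it. The exclusion in the end-of-study questionnaire belongs to a question about the whole period and should not be carried over.
- As a small accompanying edit, limit the wording on current discomfort to the two later times, so that the 15-minute mark reports insertion pain as the site and subject instructions both intend.

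Cumulative discomfort stays in the end-of-study part of Appendix D, which already asks for it. The cost is one form revision, with no added visits, samples or subjects.
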